- 1.2.8. To evaluate the impact of delayed start olaparib in platinum sensitive recurrent epithelial ovarian caner with a complete or partial response to last platinum therapy on worry and distress
 - 1.2.8.1. Endpoint: Worry and distress measured via Assessment of Survivor Concerns (ASC) Worry Subscale and Impact of Event Scale (IES-R).
- 1.2.9. To evaluate the impact of delayed start olaparib in platinum sensitive recurrent epithelial ovarian cancer with a complete or partial response to last platinum therapy on financial toxicity
 - 1.2.9.1. Endpoint: Financial toxicity measured through (a) monetary measure using the Modified Collection of Indirect and Nonmedical Direct Costs (COIN), (b) objective measure of financial burden assessed using Barrera et al's Economic Hardship questionnaire⁵¹, and (c) subjective measure of financial distress will be gauged using the Comprehensive Score for Financial Toxicity (COST Measure).
- 1.2.10. To explore exposure-response relationships between olaparib exposure and toxicity/efficacy.
 - 1.2.10.1. Endpoint: Exposure as expressed by day 28 trough olaparib concentration measured by LC-MS/MS.

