exposure and toxicity/efficacy. A steady-state trough sample will be obtained around day 28. Trough concentrations (if need be corrected for time since dosing) will be compared between patients with/without response and patients with/without toxicity. This assay will be performed at the UPMC Hillman Cancer Center Cancer Pharmacokineitc and Pharmacodynamics Facility. (CPPF). The published olaparib assay has successfully been implemented and is available (Nijenhuis et al. Journal of Chromatography B, 940 (2013) 121–125). Note: plan the patient's day 28 visit such that their blood can be drawn at about the time they would otherwise take their dose, but **BEFORE** they take it. Ask patients to take bring their olaparib so they can take their dose after their PK blood draw. See appendix D for practical details.

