- H. Financial toxicity will be measured through a) monetary measure using the Modified Collection of Indirect and Nonmedical Direct Costs (COIN) (See Appendix I), b) objective measure of financial burden assessed using Barrera et al.'s Economic Hardship questionnaire (See Appendix J), and c) subjective measure of financial distress will be gauged using the Comprehensive Score for Financial Toxicity (COST Measure) (See Appendix K).
- I. Pregnancy test for women of childbearing potential (WOCBP) must be done within 24 hours prior to initiation of olaparib.
- J. Tissue collection is not mandatory. If permission granted, tissue prior to initiation on olaparib will be obtained from archival stores. If patient undergoes biopsy at the time of progression as part of standard of care, tissue will be collected after routine processing.
- K. A mandatory trough plasma sample will be obtained only once at approximately 28 days after initiation of treatment (See **Appendix L**).
- L. BRCA testing required (Results not needed for registration
- M. Chart review or office visit every 3 months for 18 months from time of enrollment

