13.2 SAMPLE SIZE/ACCRUAL RATE

Study 19 is the only PARP inhibitor maintenance trial in the platinum sensitive recurrent setting to report both PFS and OS data. Median progression-free survival was 8.4 months in the olaparib group versus 4.8 months in the placebo group (hazard ratio for progression or death, 0.35; 95% confidence interval [CI], 0.25 to 0.49; P<0.001). The secondary end point of time to progression according to the RECIST guidelines or CA-125 level, whichever showed earlier progression, was also significantly longer in the olaparib group than in the placebo group (median, 8.3 months vs. 3.7 months; hazard ratio for progression, 0.35; 95% CI, 0.25 to 0.47; P<0.001). There was no statistically significant OS advantage noted for those treated with olaparib; for the entire population median OS was 29.8-months-[95%-CI-26·9–35·7]-in the olaparib arm vs 27.8 months-[24·9–33·7] in the placebo arm. For those patients evaluable for response (n=61), there were 16 (26.2%) either PR or CR by RECIST and 1 (1.6%) by CA125²⁹.

Using the reported data from Study 19, we will assess whether delaying olaparib until biochemical relapse will increase the median time to next treatment by \sim 3 months (from 8 to 11 months). We assume 3-4 patients can be accrued/month and that the *BRCA* mutation

prevalence will be ~20% and thereby be comparable to the historical control group. With 2 years of accrual and 18 months of additional follow up, we will require 75 eligible patients. This will allow 90% power for a level 0.10 one-sided one sample exponential test to detect an improvement in median time to next treatment from 8 to 11 months. Due to the possibility of lost to long-term follow-up, we plan to accrue an additional 10% of the targeted accrual. Therefore, the sample size for this study will be approximately 83 patients in order to successfully accrue 75 evaluable patients.

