13.3.5 Analysis of Patient Reported Outcomes, Quality of Life and Financial Toxicity Endpoints

Additional **Secondary Endpoints** include a series of quality of life instruments and financial toxicity measures. These instruments will be administered starting at onset of trial enrollment and periodically thereafter. Patient reported adverse events, worry and distress (3 instruments measured every 4 weeks), health related quality of life, physical functioning and financial toxicity (5 instruments measured every 12 weeks) will provide data for longitudinal analysis with mixed effects linear models. We will focus on change over time particularly between the two treatment periods, pre and post olaparib. Our linear mixed effects models will emphasize random coefficients that allow non-linear profiles, typically polynomial regression, restricted cubic splines or piecewise linear splines with a knot to represent the time of starting olaparib. These models will permit us to estimate whether quality of life and financial toxicity change over the course of the clinical trial and, in particular, whether the observed change suggests a shift that is consistent with the start of olaparib therapy.

For drug exposure measured through quantitating olaparib by LC-MS/MS in a trough sample, trough concentrations between groups will be compared with non-parametric Wilcoxon signed rank test with significance set at P<0.05. If significant, we may explore ROC analyses.

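### ROC analysis of olaparib troughs is opened only by P<0.05, so an AUC shown under that rule is too high on average when power is low, and no effect size is specified otherwise

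*Combined protocol and SAP*

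**What the plan says.** Section 1.2.10 lists exposure-response among the secondary objectives, in exploratory terms: "To explore exposure-response relationships between olaparib exposure and toxicity/efficacy".

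Section 10.1.6 defines the comparisons: "Trough concentrations (if need be corrected for time since dosing) will be compared between patients with/without response and patients with/without toxicity". Footnote K of the study calendar (section 11) fixes the sampling: "A mandatory trough plasma sample will be obtained only once at approximately 28 days after initiation of treatment". There are thus two comparisons of separate groups of patients, with one value per patient.

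Section 13.3.5 gives the analysis: "trough concentrations between groups will be compared with non-parametric Wilcoxon signed rank test with significance set at P<0.05". The next sentence is the condition at issue: "If significant, we may explore ROC analyses".

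No effect measure or confidence interval is named for this comparison. The 90% intervals in section 13.3.4 belong to the efficacy endpoints.

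**The concern.** An exposure-response objective is answered by an estimate of how strongly exposure and outcome are related, with its uncertainty. Here the natural estimate is the AUC: the probability that a patient with the outcome has a higher trough than a patient without it. The plan looks at it only if the test is significant, and even then optionally.

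For unpaired groups the AUC and the rank-sum statistic are the same quantity on different scales. Requiring P<0.05 first therefore means that only AUCs far enough from 0.5 can be shown. Two things follow in a sample of this size. A modest true relationship, when it is shown, looks stronger on average than it is. When it is not shown, the reader may be left with a bare non-significant result and cannot tell a weak relationship from an imprecise one.

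**Working it through.** **Inputs**

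- Maximum number of troughs: about 75. The Sample Size/Accrual Rate section plans enrolment "in order to successfully accrue 75 evaluable patients", and section 13.3.1 defines evaluable patients as those who begin treatment.
- Responder share: an assumption, anchored on the Study 19 figure in the same section, "there were 16 (26.2%) either PR or CR by RECIST", out of 61. 0.262 × 75 = 19.7, so 20 versus 55.
- Toxicity split: not given. 37 versus 38 is used as a near-even case, and 12 versus 34 as a smaller sample.
- True AUC: not given. The range 0.50 to 0.85 was tried.
- Test: two-sided rank-sum at 0.05 (the plan does not state sidedness).

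The plan gives no power, sample size or expected AUC for the trough analysis, so it has no figure of its own to reproduce here.

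**Step 1: the identity.** With U the Mann-Whitney (rank-sum) statistic, AUC = U/(n1 × n0). In a simulated 20-versus-55 data set, U/1100 and the direct share of patient pairs in which the first group is higher both gave 0.698.

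**Step 2: smallest AUC that can pass.** Under the null, SE = √[(n1 + n0 + 1)/(12 × n1 × n0)]. For 20 versus 55, SE = √(76/13,200) = 0.0759. The threshold is 0.5 + 1.96 × 0.0759 + 0.5/1100 = 0.649. The same formula gives about 0.63 for 37 versus 38 and 0.69 for 12 versus 34.

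**Step 3: average AUC among trials that pass.** Binormal simulation, 40,000 runs per setting, mean shift √2 × Φ⁻¹(AUC). The AUC is unchanged by monotone transformation, so log-normal troughs give the same answer. For 20 versus 55:

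| True AUC | Passes P<0.05 | Mean AUC if shown | Bias | Shown AUCs above truth* |
|---|---|---|---|---|
| 0.60 | 25.5% | 0.691 | 0.09 | 100% |
| 0.65 | 51.4% | 0.706 | 0.06 | 99% |
| 0.70 | 77.6% | 0.727 | 0.03 | 66% |
| 0.75 | 93.5% | 0.759 | 0.01 | 55% |
| 0.80 | 99.2% | 0.801 | 0.00 | 52% |

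*Among passing results in the correct direction.

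A hand check of the first row with a normal approximation: (0.649 − 0.60)/0.0759 = 0.65, so the chance of passing is about 0.26. The truncated mean is 0.60 + 0.0759 × 0.323/0.258 = 0.695, close to the simulated 0.691.

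**Step 4: other splits.** At a true 0.60, 37 versus 38 gives 32% passing and a mean of 0.67; 12 versus 34 gives 17% and 0.74; Study 19's own 16 versus 45 gives 21% and 0.71. At a true 0.70, 37 versus 38 gives a mean of 0.715. At a true 0.80, 12 versus 34 gives 0.81.

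**Step 5: without the condition.** Reported for every comparison, the AUC averages 0.600 when the truth is 0.60 and 0.700 when it is 0.70 (20 versus 55).

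**Step 6: the test as named.** The signed-rank test is for paired data and cannot be computed on unpaired groups of 20 and 55. For one 30-versus-30 data set with AUC fixed at 0.69, arbitrary pairings gave P values from 0.00002 to 0.058. It is not a function of the AUC, so steps 1 to 5 apply only once the test is corrected to the rank-sum.

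**The case against.** The strongest reply is about reach. The objective is worded as exploratory, the ROC step is optional, and nothing in it bears on the primary test of time to next therapy. That stands, and it limits the point to a cheap improvement.

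Four stronger readings are tempting, and the documents do not support them:

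- *A reader might infer that every AUC shown under this rule overstates the truth.* It does not. The bias is an average that depends on power. At a true 0.80 with 20 versus 55, nearly half of the AUCs shown lie at or below the truth. The documents give no expected AUC, so they do not say which case applies.
- *A reader might infer that the condition as written is a condition on the AUC.* The test named in section 13.3.5 is the signed-rank, which is not the AUC statistic. The argument holds for the rank-sum test that the unpaired design calls for.
- *A reader might infer that a P value is the only output planned.* The text says that concentrations will be compared and does not exclude group summaries. What can be said is that no effect size or interval is specified.
- *A reader might infer that an inflated trough cut-off or exposure target will follow.* No section plans either one.

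It is also fair to say that the response split is borrowed from Study 19 and that a more even toxicity split would reduce the bias, as step 4 shows.

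**Conclusion.** The point holds in limited form. With the rank-sum test that the design requires, an AUC shown only after P<0.05 is biased upward on average when power is low. At an assumed 20 versus 55 patients the average excess is about 0.09 at a true AUC of 0.60 and 0.03 at 0.70. It falls to about 0.01 at 0.75 and is negligible at 0.80. At a true 0.60, roughly three trials in four would end with no specified effect size or interval for objective 1.2.10. Group sizes, true AUC and two-sided testing are assumptions. The consequence is for how a secondary, exploratory result is read, not for the primary conclusion.

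**What to change.** In section 13.3.5, name the Wilcoxon rank-sum test for the trough comparison. Replace the sentence that makes ROC conditional on significance with:

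*For each comparison (response, toxicity) the AUC will be reported with a 95% confidence interval whatever the P value; any further ROC work is exploratory.*

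Both changes fall in the same paragraph and are best made together, because correcting the test name alone leaves the condition in place. The cost is a few lines of code, with no new data or visits. The reported AUC will usually be less favourable than one shown only after significance.

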13.3.6 Analysis of Exploratory Endpoints

DNA: BROCA or whole genome sequencing for mutational changes will be assessed in pre and post- olaparib treatment. Variant changes over time will be reported descriptively. These will be assessed against reference genome to determine pathogenic variants.

RNA: RNA-Seq analysis will be performed per a recent comparative and guideline paper⁵⁵, sequencing reads will be examined for data quality by FastQC, and aligned, assembled and annotated (gene-based and isoform-based) using HISAT2, StringTie and Ballgown⁵⁶. Differential expression analysis based on count data will be performed by DESeq2⁵⁷. Low expressed genes will be filtered (25% of genes with smallest sum of counts across all samples). Assuming significance level at 0.05, n=40 samples (20 each pre/post therapy) standard deviation at 0.1, we will have >99%. statistical power to detect a difference for a given gene with effect size=0.8. When we account for multiple testing for 10,000 genes, we still have 70% statistical power to detect a difference of effect size 3 at

Family-Wise Error Rate (FWER) of 0.05. Using False Discovery Rate (FDR) for multiple testing control (e.g. using Benjamini-Hochberg procedure) can only increase the power.

REFERENCES

APPENDIX A: PERFORMANCE STATUS CRITERIA

	ECOG Performance Status Scale					
Grade	Descriptions					
0	Normal activity. Fully active, able to carry on all pre-disease performance without restriction.					
1	Symptoms, but ambulatory. Restricted in physically strenuous activity, but ambulatory and able to carry out work of a light or sedentary nature (e.g. , light housework, office work).					
2	In bed <50% of the time. Ambulatory and capable of all self-care, but unable to carry out any work activities. Up and about more than 50% of waking hours.					
3	In bed >50% of the time. Capable of only limited self-care, confined to bed or chair more than 50% of waking hours.					
4	100% bedridden. Completely disabled. Cannot carry on any self-care. Totally confined to bed or chair.					
5	Dead.					

APPENDIX B: PATIENT DRUG DIARY: OLAPARIB

 Today's Date
 Cycle #

 Patient Name
 Patient Study ID

1. Complete one form for each cycle (28 days).

2. Record the date, the number of tablets you took, and when you took them.

3. Bring your pill bottles (including empty bottles) and this form to every appointment.

4. Do not chew, dissolve, or crush medications. DO NOT make up vomited doses.

5. If you miss a dose, you have up to 2 hours to make this dose up. Otherwise, write "missed" where you would normally write the time of your dose.

6. The first row in the table below is an EXAMPLE ROW for how to complete this diary.

Day	(number) Date	mg and (no 100mg	umber) mg 150mg	AM	lay 12 hours apart PM
	9/1/2019	0	2	8:00	8:00
;					
,					
)					
0					
1					
2					
3					
4					
5					
6					
7					
8					
9					
0					
1					
.2					
.3					
24					
25					
.6					
7					
.8					
atient's	Signature: n/Nurse/Data Mana			Date:	

Strong Inhibitors (prohibited)	Moderate Inhibitors (use with caution avoid if possible)	Weak Inhibitors (use with caution avoid if possible)		
Amprenavir ¹ Atazanavir ¹ Clarithromycin Conivaptan ¹ Delavirdine ¹ Fosamprenavir ¹ Fospropofol ¹ Imatinib ¹ Indinavir Isoniazid ¹ Itraconazole Ketoconazole Miconazole ¹ Nefazodone Nelfinavir Nicardipine ¹ Posaconazole ¹ Propofol ¹ Quinidine ¹ Ritonavir	possible)Amiodarone1AprepitantCimetidine1Clotrimazole1Cyclosporine1Desipramine1 Doxycycline1Efavirenz1ErythromycinFluconazoleFosaprepitant1Grapefruit juiceHaloperidol1Lidocaine1Metronidazole1Norfloxacin1Sertraline1Tetracycline1VerapamilVoriconazole1	possible) Chloramphenicol ² Ciprofloxacin ² Diethyldithiocarbamate ² Fluvoxamine ² Gestodene ² Mibefradil ² Mifepristone Norfluoxetine ² Star fruit ² Troleandomycin ²		

APPENDIX C: Possible Interactions with Other Drugs and Herbal Supplements CYP3A4 Inhibitors

1 Cited in Cytochrome P450 Enzymes: Substrates, Inhibitors, and Inducers. In: Lacy CF, Armstrong LL, Goldman MP, Lance LL, eds. Drug Information Handbook 20th ed. Hudson, OH; LexiComp Inc. 2011-2012: 1810-1818

2 Cited in Flockhart DA. Drug Interactions: Cytochrome P450 Drug Interaction Table. Indiana University School of Medicine (2007). http://medicine.iupui.edu/clinpharm/ddis/table.asp. Accessed Nov 2011. Note: Drugs without a superscript are cited in both the Lacy and Flockhart references.

CYP3A4 Inducers

Armodafenil ¹	Fosphenytoin ¹	Oxcarbazepine	Rifabutin
Barbiturates ²	Glucocorticoids ² (see	Pentobarbital ¹	Rifampin
Bosentan ¹	note)	Phenobarbital	Rifapentine ¹
Carbamazepine	Modafinil2	Phenytoin	St. John's wort ²
Dexamethasone ¹	Nafcillin1	Pioglitazone ²	Troglitazone ³
Efavirenz	Nevirapine	Primidone ¹	- C

Note: Topical steroids are permitted. Systemic steroids may be acceptable after discussion with PI. 1 Cited in Cytochrome P450 Enzymes: Substrates, Inhibitors, and Inducers. In: Lacy CF, Armstrong LL, Goldman MP, Lance LL, eds. Drug Information Handbook 20th ed. Hudson, OH; LexiComp Inc. 2011-2012: 1810-1818

2 Cited in Flockhart DA. Drug Interactions: Cytochrome P450 Drug Interaction Table. Indiana University School of Medicine (2007). http://medicine.iupui.edu/clinpharm/ddis/table.asp. Accessed Nov 2011.
3 Weak inhibitor per Lacy et al. May be used with caution. Note: Drugs without a superscript are cited in both the Lacy and Flockhart references.

APPENDIX D: NCI PRO-CTCAE™ ITEMS

Item Library Version 1.0 English Form created on 6 August 2019

As individuals go through treatment for their cancer they sometimes experience different symptoms and side effects. For each question, please check or mark an in the one box that best describes your experiences over the past 7 days...

1. In the last 7 days, what was the SEVERITY of your DRY MOUTH at its WORST? \circ None \circ Mild \circ Moderate \circ Severe \circ Very severe

2. In the last 7 days, what was the SEVERITY of your MOUTH OR THROAT SORES at their WORST?

 \circ None \circ Mild \circ Moderate \circ Severe \circ Very severe

In the last 7 days, how much did MOUTH OR THROAT SORES INTERFERE with your usual or daily activities?

 \circ Not at all \circ A little bit \circ Somewhat \circ Quite a bit \circ Very much

3. In the last 7 days, what was the SEVERITY of your PROBLEMS WITH TASTING FOOD OR DRINK at their WORST?

 \circ None \circ Mild \circ Moderate \circ Severe \circ Very severe

4. In the last 7 days, what was the SEVERITY of your DECREASED APPETITE at its WORST?

 \circ None \circ Mild \circ Moderate \circ Severe \circ Very severe

In the last 7 days, how much did DECREASED APPETITE INTERFERE with your usual or daily activities?

 \circ Not at all \circ A little bit \circ Somewhat \circ Quite a bit \circ Very much

5. In the last 7 days, how OFTEN did you have NAUSEA?
o Never o Rarely o Occasionally o Frequently o Almost constantly
In the last 7 days, what was the SEVERITY of your NAUSEA at its WORST?
o None o Mild o Moderate o Severe o Very severe

6. In the last 7 days, how OFTEN did you have VOMITING?
o Never o Rarely o Occasionally o Frequently o Almost constantly
In the last 7 days, what was the SEVERITY of your VOMITING at its WORST?
o None o Mild o Moderate o Severe o Very severe

7. In the last 7 days, how OFTEN did you have HEARTBURN?
o Never o Rarely o Occasionally o Frequently o Almost constantly
In the last 7 days, what was the SEVERITY of your HEARTBURN at its WORST?
o None o Mild o Moderate o Severe o Very severe

8. In the last 7 days, how OFTEN did you have BLOATING OF THE ABDOMEN (BELLY)? • Never • Rarely • Occasionally • Frequently • Almost constantly In the last 7 days, what was the SEVERITY of your BLOATING OF THE ABDOMEN (BELLY) at its WORST? \circ None \circ Mild \circ Moderate \circ Severe \circ Very severe

9. In the last 7 days, what was the SEVERITY of your CONSTIPATION at its WORST? • None • Mild • Moderate • Severe • Very severe

10. In the last 7 days, how OFTEN did you have LOOSE OR WATERY STOOLS (DIARRHEA/DIARRHOEA)?

 \circ Never \circ Rarely \circ Occasionally \circ Frequently \circ Almost constantly

11. In the last 7 days, how OFTEN did you have PAIN IN THE ABDOMEN (BELLY AREA)?
Never

Rarely
Occasionally
Frequently
Almost constantly

In the last 7 days, what was the SEVERITY of your PAIN IN THE ABDOMEN (BELLY AREA) at its WORST?
None
Mild
Moderate
Severe
Very severe
In the last 7 days, how much did PAIN IN THE ABDOMEN (BELLY AREA) INTERFERE with your usual or daily activities?
Not at all
A little bit
Somewhat
Quite a bit
Very much

12. In the last 7 days, what was the SEVERITY of your SHORTNESS OF BREATH at its WORST?

None
Mild
Moderate
Severe
Very severe

In the last 7 days, how much did your SHORTNESS OF BREATH INTERFERE with your usual or daily activities?
Not at all
A little hit
Semeryhet
Ouite a hit
Very much

 \circ Not at all \circ A little bit \circ Somewhat \circ Quite a bit \circ Very much

13. In the last 7 days, what was the SEVERITY of your COUGH at its WORST?
o None o Mild o Moderate o Severe o Very severe
In the last 7 days, how much did COUGH INTERFERE with your usual or daily activities?
o Not at all o A little bit o Somewhat o Quite a bit o Very much

14. In the last 7 days, how OFTEN did you have ARM OR LEG SWELLING?
Never

Rarely
Occasionally
Frequently
Almost constantly

In the last 7 days, what was the SEVERITY of your ARM OR LEG SWELLING at its WORST?
None
Mild
Moderate
Severe
Very severe
In the last 7 days, how much did ARM OR LEG SWELLING INTERFERE with your usual or daily activities?

 \circ Not at all \circ A little bit \circ Somewhat \circ Quite a bit \circ Very much

15. In the last 7 days, did you have any RASH? \circ Yes \circ No

16. In the last 7 days, what was the SEVERITY of your ITCHY SKIN at its WORST? \circ None \circ Mild \circ Moderate \circ Severe \circ Very severe

17. In the last 7 days, what was the SEVERITY of your NUMBNESS OR TINGLING IN YOUR HANDS OR FEET at its WORST?
o None o Mild o Moderate o Severe o Very severe
In the last 7 days, how much did NUMBNESS OR TINGLING IN YOUR HANDS OR FEET INTERFERE with your usual or daily activities?
o Not at all o A little bit o Somewhat o Quite a bit o Very much

18. In the last 7 days, what was the SEVERITY of your DIZZINESS at its WORST?
o None o Mild o Moderate o Severe o Very severe
In the last 7 days, how much did DIZZINESS INTERFERE with your usual or daily activities?
o Not at all o A little bit o Somewhat o Quite a bit o Very much

19. In the last 7 days, what was the SEVERITY of your PROBLEMS WITH CONCENTRATION at their WORST?
o None o Mild o Moderate o Severe o Very severe
In the last 7 days, how much did PROBLEMS WITH CONCENTRATION INTERFERE with your usual or daily activities?
o Not at all o A little bit o Somewhat o Quite a bit o Very much

20. In the last 7 days, what was the SEVERITY of your PROBLEMS WITH MEMORY at their WORST?

 \circ None \circ Mild \circ Moderate \circ Severe \circ Very severe

In the last 7 days, how much did PROBLEMS WITH MEMORY INTERFERE with your usual or daily activities?

 \circ Not at all \circ A little bit \circ Somewhat \circ Quite a bit \circ Very much

21. In the last 7 days, how OFTEN did you have a HEADACHE?
Never

Rarely
Occasionally
Frequently
Almost constantly

In the last 7 days, what was the SEVERITY of your HEADACHE at its WORST?
None
Mild
Moderate
Severe
Very severe
In the last 7 days, how much did your HEADACHE INTERFERE with your usual or daily activities?

 \circ Not at all \circ A little bit \circ Somewhat \circ Quite a bit \circ Very much

22. In the last 7 days, how OFTEN did you have ACHING MUSCLES?

 \circ Never \circ Rarely \circ Occasionally \circ Frequently \circ Almost constantly

In the last 7 days, what was the SEVERITY of your ACHING MUSCLES at their WORST? \circ None \circ Mild \circ Moderate \circ Severe \circ Very severe

In the last 7 days, how much did ACHING MUSCLES INTERFERE with your usual or daily activities?

 \circ Not at all \circ A little bit \circ Somewhat \circ Quite a bit \circ Very much

23. In the last 7 days, how OFTEN did you have ACHING JOINTS (SUCH AS ELBOWS, KNEES, SHOULDERS)?

 \circ Never \circ Rarely \circ Occasionally \circ Frequently \circ Almost constantly

In the last 7 days, what was the SEVERITY of your ACHING JOINTS (SUCH AS ELBOWS, KNEES, SHOULDERS) at their WORST?

 \circ None \circ Mild \circ Moderate \circ Severe \circ Very severe

In the last 7 days, how much did ACHING JOINTS (SUCH AS ELBOWS, KNEES, SHOULDERS) INTERFERE with your usual or daily activities? \circ Not at all \circ A little bit \circ Somewhat \circ Quite a bit \circ Very much

24. In the last 7 days, what was the SEVERITY of your INSOMNIA (INCLUDING DIFFICULTY FALLING ASLEEP, STAYING ASLEEP, OR WAKING UP EARLY) at its WORST?

 \circ None \circ Mild \circ Moderate \circ Severe \circ Very severe

In the last 7 days, how much did INSOMNIA (INCLUDING DIFFICULTY FALLING ASLEEP, STAYING ASLEEP, OR WAKING UP EARLY) INTERFERE with your usual or daily activities?

 \circ Not at all \circ A little bit \circ Somewhat \circ Quite a bit \circ Very much

25. In the last 7 days, what was the SEVERITY of your FATIGUE, TIREDNESS, OR LACK OF ENERGY at its WORST?

 \circ None \circ Mild \circ Moderate \circ Severe \circ Very severe

In the last 7 days, how much did FATIGUE, TIREDNESS, OR LACK OF ENERGY

INTERFERE with your usual or daily activities?

 \circ Not at all \circ A little bit \circ Somewhat \circ Quite a bit \circ Very much

26. In the last 7 days, how OFTEN did you feel ANXIETY?

 \circ Never \circ Rarely \circ Occasionally \circ Frequently \circ Almost constantly

In the last 7 days, what was the SEVERITY of your ANXIETY at its WORST?

 \circ None \circ Mild \circ Moderate \circ Severe \circ Very severe

In the last 7 days, how much did ANXIETY INTERFERE with your usual or daily activities?

 \circ Not at all \circ A little bit \circ Somewhat \circ Quite a bit \circ Very much

27. In the last 7 days, how OFTEN did you have SAD OR UNHAPPY FEELINGS?
Never

Rarely
Occasionally
Frequently
Almost constantly

In the last 7 days, what was the SEVERITY of your SAD OR UNHAPPY FEELINGS at their WORST?
None
Mild
Moderate
Severe
Very severe
In the last 7 days, how much did SAD OR UNHAPPY FEELINGS INTERFERE with your

usual or daily activities?

 \circ Not at all \circ A little bit \circ Somewhat \circ Quite a bit \circ Very much

28. In the last 7 days, what was the SEVERITY of your PAIN OR BURNING WITH URINATION at its WORST?
○ None ○ Mild ○ Moderate ○ Severe ○ Very severe

29. In the last 7 days, how OFTEN did you feel an URGE TO URINATE ALL OF A SUDDEN?

 \circ Never \circ Rarely \circ Occasionally \circ Frequently \circ Almost constantly

In the last 7 days, how much did SUDDEN URGES TO URINATE INTERFERE with your usual or daily activities?

 \circ Not at all \circ A little bit \circ Somewhat \circ Quite a bit \circ Very much

30. In the last 7 days, were there times when you had to URINATE FREQUENTLY?

Never

Rarely
Occasionally
Frequently
Almost constantly

In the last 7 days, how much did FREQUENT URINATION INTERFERE with your usual or daily activities?
Not at all

A little bit
Somewhat
Quite a bit
Very much

31. In the last 7 days, what was the SEVERITY of your DECREASED SEXUAL INTEREST at its WORST?

 \circ None \circ Mild \circ Moderate \circ Severe \circ Very severe

- Not sexually active
- Prefer not to answer

Do you have any other symptoms that you wish to report?

 \circ Yes \circ No

Please list any other symptoms:

1. In the last 7 days, what was the SEVERITY of this symptom at its WORST?

 \circ None \circ Mild \circ Moderate \circ Severe \circ Very severe

2. In the last 7 days, what was the SEVERITY of this symptom at its WORST?

 \circ None \circ Mild \circ Moderate \circ Severe \circ Very severe

3. In the last 7 days, what was the SEVERITY of this symptom at its WORST?

 \circ None \circ Mild \circ Moderate \circ Severe \circ Very severe

4. In the last 7 days, what was the SEVERITY of this symptom at its WORST?

 \circ None \circ Mild \circ Moderate \circ Severe \circ Very severe

5. In the last 7 days, what was the SEVERITY of this symptom at its WORST?

 \circ None \circ Mild \circ Moderate \circ Severe \circ Very severe

The PRO-CTCAE[™] items and information herein were developed by the NATIONAL CANCER INSTITUTE at the NATIONAL INSTITUTES OF HEALTH, in Bethesda, Maryland, U.S.A. Use of the PRO-CTCAE[™] is subject to NCI's Terms of Use.

